5.2.1.4 Study Drug Exposure

Exposure analyses will be based on the actual dose administered (in mg) and body weight (in kg) per the eCRF. The baseline body weight will be used for calculating the cumulative dose unless the subject's weight changes $\geq 10\%$. For subjects with a weight change $\geq 10\%$, the revised weight will be used from the time point of the change and onwards.

For analysis of dose exposure **across all cycles** the following definitions will be used:

- **Duration of cycle:**
 - **Patients discontinuing during first cycle:** Duration of cycles (in weeks)² = $(\text{Date of last dose} - \text{date of first dose} + 21) / 7$
 - **Patients discontinuing treatment after start of Cycle 2:** Duration of cycles (in weeks)³ = $(\text{Date of last dose} - \text{date of first dose} + 7) / 7$
- Duration of treatment:
 - **Patients discontinuing during first cycle:** Duration of treatment (in weeks)⁴ = $(\text{Date of last dose} - \text{date of first dose} + 7) / 7$

² 21 days added to duration of cycle because of a 2 week observation period after last dose in cycle 1 (ie, 21 days until the next dose).

³ 7 days added to duration of cycle because administrations are planned every week (starting from Cycle 2).

⁴ 7 days added to duration of treatment because administrations are planned every week. Duration of treatment does not include the 2-week observation period in Cycle 1.

- **Patients discontinuing treatment after start of Cycle 2:** Duration of treatment (in weeks)⁵ = Duration of cycle -14
- Cumulative dose (mg/kg) = Sum of all [administered dosages (mg) / baseline weight⁶ (kg)]
- Dose intensity (mg/kg/week) = Cumulative dose / Duration of treatment
- Planned weekly dose: Refer to Table 1: Planned Dose Regimens
- Relative dose intensity (%) = (Dose intensity / Planned weekly dose) * 100.
- Number of dose reductions: total number of reduction steps comparing the intended dose level before each infusion (as entered in the eCRF) to the protocol planned dose level as referenced in Table 2: General Dose Reduction Guidelines.
- Dose delay within a cycle: a dose is considered delayed if it is administered more than 3 days after the scheduled date relative to the previous administration.

Table 1: Planned Dose Regimens

Cohort	All cycles	Dosing Frequency
1	2.5 mg/kg	Weekly
2	0.3 mg/kg	Weekly
3	0.6 mg/kg	Weekly
4	1.25 mg/kg	Every 2 weeks
5	1.25 mg/kg	Weekly
6	2.5 mg/kg	Every 2 weeks

For analysis of dose exposure **in Cycle 1 only** the same definitions as across all cycles will be used except the following:

- Duration of cycles (in weeks)⁷ = (Date of last dose – date of first dose+21) / 7
Or if start of cycles 2⁸ occurs before last dose of cycle 1 + 21 days:
Duration of cycles (in weeks)= (Date of start Cycle 2-date of first dose)/7

⁵ 14 days is subtracted from the duration of cycle because the 2-week observation period is excluded from the duration of treatment.

⁶ Except in case of weight change from baseline $\geq 10\%$ as described above.

⁷ 21 days added to duration of cycle, because of a 2-week observation period after last dose in Cycle 1 (i.e. 21 days until the next dose).

⁸ Start of Cycle 2 is defined as day of first infusion of Cycle 2.

- Cumulative dose (mg/kg) = Sum of [all administered dosages during cycle 1 (mg) / baseline weight (kg)]

Table 2: General Dose Reduction Guidelines

Cohort	Planned Starting dose	First Reduction	Second Reduction
1	2.5 mg/kg weekly	Discontinue IMC-CS4	-
2	0.3 mg/kg weekly	Discontinue IMC-CS4	-
3	0.6 mg/kg weekly	0.3 mg/kg weekly	Discontinue IMC-CS4
4	1.25 mg/kg every 2 weeks	0.6 mg/kg every 2 weeks	0.3 mg/kg every 2 weeks
5	1.25 mg/kg weekly	0.6 mg/kg weekly	0.3 mg/kg weekly
6	2.5 mg/kg every 2 weeks	1.25 mg/kg every 2 weeks	0.6 mg/kg every 2 weeks

Note: Actual dose levels entered in the CRF will be rounded to the nearest dose level listed in this table (e.g. any IMC-CS4 dose level >5 and < 7.5 mg/kg will be rounded to 5 mg/kg for the purpose of the dose reduction calculation). No dose reductions are allowed after a DLT. In the setting of non-life-threatening reversible Grade ≤ 3 IMC-CS4-related toxicities that do not meet the definition of a DLT, IMC-CS4 may be held (if appropriate in the opinion of the Investigator) for a maximum of 3 weeks, until resolution to Grade < 2 .

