5.2 Definitions and data handling conventions

5.2.1 Safety Data Handling and Definitions

5.2.1.1 Coding

- **Adverse events:** All adverse events (AE) will be coded by the Medical Dictionary for Regulatory Activities (MedDRA™) and graded according to the National Cancer Institute (NCI) Common Terminology Criteria for Adverse Events (CTCAE), Version 4.0 (version 4.0 includes all of the minor versions 4.0x).

¹ i.e. first four infusions completed, plus an observation period of 21 days after last dose in cycle 1 or entry into cycle 2 if start of cycle 2 occurs before completion of the 21 days observation.
IMC-CS4 (LY3022855)

- **Pre treatment Therapy and Concurrent Therapy:** Current medications, medications taken within 30 days prior to first dose of study therapy, prior cancer therapy will be coded using the WHOdrug.

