5.3.4 Analyses of Safety Data

5.3.4.1 Study Drug Exposure

The following variables will be summarized according to the definitions provided in section 5.2.1.4. Exposure analyses will include the following:

Cycle 1 only using the MTD population:

- Number of infusions
- Cumulative dose (mg/kg)
- Dose intensity (mg/kg/week)
- ~~Adjusted dose intensity (mg/kg/week)~~
- Relative dose intensity (%)
- Number (%) of subjects with dose modifications (reduced or change of infusion rate).

Across all cycles using the Safety population

- Duration of treatment (weeks)
- Duration of cycles (weeks)
- Number (%) of subjects treated by cycle.
- Number of infusions
- Cumulative dose (mg/kg)
- Dose intensity (mg/kg/week)
- Adjusted dose intensity (mg/kg/week)
- Relative dose intensity (%)
- Number (%) of subjects with dose modifications (reduced or change of infusion rate).

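### SAP 5.2.1.4 applies weekly-dosing constants to every-2-week Cohort 4: its relative dose intensity is misstated and, on the current schedule, its Cycle 1 AE and DLT window closes early

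*SAP*

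**What the plan says.** **Durations.** For a subject who stops in Cycle 1, SAP 5.2.1.4 defines duration of treatment as (last dose − first dose + 7)/7 weeks, because "7 days added to duration of treatment because administrations are planned every week" (footnote 4). For a subject who stops later, the rule is "Duration of treatment (in weeks)⁵ = Duration of cycle -14". Footnote 5 explains: "14 days is subtracted from the duration of cycle because the 2-week observation period is excluded from the duration of treatment". Duration of cycle adds 21 days in Cycle 1 and 7 days afterwards, again on weekly and 2-week-observation grounds (footnotes 2 and 3).

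**Dose intensity.** Dose intensity is cumulative dose over duration of treatment. Relative dose intensity divides that by the planned weekly dose, for which the text says "Planned weekly dose: Refer to Table 1: Planned Dose Regimens". That table lists dose per infusion and frequency. Cohort 4 is 1.25 mg/kg every 2 weeks and Cohort 6 is 2.5 mg/kg every 2 weeks. No per-week figure is given.

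**Cycle 1 outputs.** For Cycle 1 exposure, "the same definitions as across all cycles will be used except the following", and the exceptions cover only duration of cycle and cumulative dose. SAP 5.3.4.1 plans this as a separate output ("Cycle 1 only using the MTD population"). SAP 5.3.4.3 and 5.3.4.4 gloss Cycle 1, for AEs and DLTs, as ending 21 days after the last Cycle 1 dose and before Cycle 2.

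**DLT population.** The body of SAP 5.1.3 admits subjects who finish the first six weeks or have a first-cycle DLT. Its footnote 1 explains finishing as "first four infusions completed, plus an observation period of 21 days after last dose in cycle 1", or entry into Cycle 2 if that comes sooner.

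**Protocol.** Cohort 4 has two Cycle 1 infusions and a 3-week observation period (Table 1). DLTs count throughout Cycle 1 (4.1.4), which lasts 6 weeks (4.1). Section 12.2 requires all scheduled Cycle 1 treatments plus any observation period.

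**The concern.** The constants +7, +21 and −14 describe four weekly infusions followed by a 2-week pause. Applied to an every-2-week cohort, the last dose is credited with one week instead of two, so dose and time do not cover the same weeks. The mismatch lies inside the SAP, because its own Table 1 gives the 2-week frequency. The same template sets the Cycle 1 AE and DLT window and footnote 1.

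Protocol 4.1 names Cohort 4's regimen as the Part A MTD and says that further subjects were enrolled there to help establish the safety profile. Its exposure, Cycle 1 AE and DLT tables are therefore ones that readers will look at. A compliant subject should show 100%.

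**Working it through.** **Inputs**
- One cycle is 42 days, so Cycle 2 starts on Day 43 (protocol 4.1).
- Weekly Part A cohorts are dosed on Days 1, 8, 15 and 22 in Cycle 1, then six times per cycle (protocol Tables 1 and 2).
- Cohort 4 is dosed on Days 1 and 15, then 43, 57, 71; 85, 99, 113; 127, 141, 155 (protocol Tables 1, 3 and 8). This is the Version 7.0 schedule. The SAP was written for Version 3.0, whose Cycle 1 infusion count is not supplied.
- Every-2-week infusions may move by 3 days either way (protocol 4.1).
- Planned weekly dose for Cohort 4 is 1.25/2 = 0.625 mg/kg/week. This is my conversion; the SAP states none.

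**1. The SAP's own 21 days.** Footnote 2 gives 21 days from the last Cycle 1 dose to the next dose. Weekly cohorts: 43 − 22 = 21, reproduced. Cohort 4: 43 − 15 = 28.

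**2. The unit.** A weekly subject completing two cycles has a last dose on Day 78 and a duration of cycle of (77 + 7)/7 = 12 weeks. Read literally, 12 − 14 = −2 weeks. Read as footnote 5 intends, 12 − 2 = 10 weeks for 10 infusions, which is 100%. Through Cycles 1, 3 and 4 the weekly durations are 4, 16 and 22 weeks for 4, 16 and 22 infusions, also 100%.

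**3. Cohort 4, full compliance, unit corrected.** T = (last − first + 7)/7, minus 2 once Cycle 2 has started.

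| Through cycle | T (weeks) | Cumulative mg/kg | mg/kg/week | vs 0.625 | vs 1.25 unconverted |
|---|---|---|---|---|---|
| 1 | (14+7)/7 = 3 | 2.5 | 0.833 | 133% | 67% |
| 2 | (70+7)/7 − 2 = 9 | 6.25 | 0.694 | 111% | 56% |
| 3 | (112+7)/7 − 2 = 15 | 10 | 0.667 | 107% | 53% |
| 4 | (154+7)/7 − 2 = 21 | 13.75 | 0.655 | 105% | 52% |

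The Cycle 1-only table gives the same first row: (14 + 21)/7 − 2 = 3 weeks.

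**4. Duration of cycle.** For Cohort 4 the SAP gives (14+21)/7 = 5, (70+7)/7 = 11, (112+7)/7 = 17 and (154+7)/7 = 23 weeks. The true spans are 6, 12, 18 and 24.

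**5. Cycle 1 window.** Weekly cohorts: Day 22 + 21 = Day 43, so all 42 days are covered. Cohort 4: Day 15 + 21 = Day 36, so Days 37 to 42 fall outside. Now let both the last Cycle 1 dose (Day 12 to 18) and the first Cycle 2 dose (Day 40 to 46) use their 3-day windows:
- Day 18 + 21 = Day 39 with Cycle 2 on Day 40 leaves 0 uncovered days.
- Day 12 + 21 = Day 33 with Cycle 2 on Day 46 leaves Days 34 to 45, which is 12 days.

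**6. Footnote 1.** Cohort 4 has two Cycle 1 infusions. At most three every-2-week infusions (Days 1, 15 and 29) fit into six weeks, so four cannot be reached under any version.

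**7. If Version 3.0 had three Cycle 1 infusions.** Day 29 + 21 = Day 50, so the window gap disappears. Cycle 1 dose intensity is 3.75/((28+7)/7) = 3.75/5 = 0.75, which is 120% of 0.625 (60% of 1.25). The exposure fault in Cycle 1 remains.

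**The case against.** **Version.** The SAP serves protocol Version 3.0. Protocol 1.4.2 confirms that Version 3.0 put Cohort 4 on every-2-week dosing, but the dosing days used here come from Version 7.0. This stands as a stated assumption. It limits the Day 36 figure and the exact percentages, not the mismatch itself, which SAP Table 1 shows on its own.

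**Size.** A reader might infer that the SAP yields no usable relative dose intensity for Cohort 4, or that compliant subjects would be reported at about half of plan. The documents do not support either. Table 1 has a frequency column, so 0.625 is a one-step conversion. On that reading the error is upward and shrinks with time. The 1.25 column in the table above requires ignoring the stated frequency; it remains possible only because no per-week value is written down.

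**Footnote 1.** Read alone, it might suggest that no DLT-free Cohort 4 subject enters the DLT population. The body of SAP 5.1.3 says otherwise and agrees with protocol 12.2. What stands is a conflict between a footnote and its own text.

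**Lost events.** Events after the window closes still enter the all-cycles AE tables on the Safety population. Only the Cycle 1 AE and DLT tables would miss them.

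**Convention.** The SAP's corrected durations of 3, 9, 15 and 21 weeks equal the weeks that the protocol does not label as observation, so the duration is defensible taken alone. No flat weekly dose matches it, however: a return of 100% would need 0.833, 0.694, 0.667 and 0.655 mg/kg/week in turn.

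**Conclusion.** The point holds and should be corrected in the SAP. The weekly constants do not fit the every-2-week cohorts. With the unit corrected and 0.625 mg/kg/week as denominator, a fully compliant Cohort 4 subject is overstated by 33, 11, 7 and 5 percentage points through Cycles 1 to 4. The Cycle 1 AE and DLT window misses 6 of 42 days when dosing is on schedule. These figures assume the Version 7.0 Cohort 4 schedule.

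The unit slip affects every cohort as printed, but footnote 5 settles its meaning.

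A reader might infer that dose decisions are at risk. The documents do not support that. Escalation follows protocol 4.1.1 and the safety reviews in 12.8, and the provisional RP2D follows 4.1.2; none of these uses the SAP's exposure formulas or its 21-day gloss. The effect is on the reported exposure, Cycle 1 AE and DLT tables. Both documents do name the DLT population as the basis for the RP2D, which is reason enough to make footnote 1 agree with its text.

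**What to change.** 1. In SAP 5.2.1.4, subtract 2 weeks instead of 14.
2. Add a per-week planned dose column to SAP Table 1, as plain conversion of the listed regimens (Cohort 4: 1.25/2 = 0.625 mg/kg/week; Cohort 6: 2.5/2 = 1.25).
3. For every-2-week cohorts, state one convention in which dose and duration cover the same weeks. One example is (last dose − first dose + 14)/7, minus 2 weeks once Cycle 2 has started. For Cohort 4 this gives 4, 10, 16 and 22 weeks for 2.5, 6.25, 10 and 13.75 mg/kg, which is 0.625 mg/kg/week and 100% each time. It counts Week 4 as treatment, although the protocol labels it observation, and the SAP should say so. If non-observation weeks are preferred, compare with the planned cumulative dose over those same weeks.
4. For every-2-week duration of cycle, add 28 days in Cycle 1 (or stop at the start of Cycle 2 if earlier) and 14 days thereafter. Cohort 4 then gives 6, 12, 18 and 24 weeks.
5. In SAP 5.3.4.3 and 5.3.4.4, define the window as the protocol's Cycle 1: through the day before the first Cycle 2 infusion, or the end of Week 6 if there is none.
6. Reword footnote 1 to follow protocol 12.2: all scheduled Cycle 1 treatments plus the observation period.

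Cost: SAP text in four places (footnote 1, 5.2.1.4, 5.3.4.3 and 5.3.4.4), one table column, and reprogramming of the Cohort 4 exposure, Cycle 1 AE and DLT tables. No protocol change and no new data.

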4 INVESTIGATIONAL PLAN

4.1 Overall Study Design and Plan

This open-label, dose-escalation, Phase 1 study will enroll a total of approximately 72 subjects to 2 parts - Parts A and B, in approximately 6 study sites in the United States. Part A consists of dose escalation of IMC-CS4 using weight-based dosing (Part A enrollment is planned to be discontinued as of 30 September 2015); Part B will consist of dose escalation of IMC-CS4 using non-weight-based dosing; the actual enrollment will depend on the number of DLTs observed and the resultant size of each cohort. Throughout this protocol, any information not indicated as “Part A only” or “Part B only” is relevant to both parts. In Part A, additional subjects were enrolled to the maximum tolerated dose (MTD) of 1.25 mg/kg q2w, in order to help establish the safety profile of IMC-CS4. In Part B, the cohort associated with the dose identified as the MTD may be expanded (up to a maximum of 12 evaluable subjects) in order to help establish the safety profile of IMC-CS4. Enrollment to the MTD expansion cohort may cease if the Sponsor (after conferring with the investigators) deems the toxicity profile precludes further enrollment. Refer also to Section [4.1.2](#).

Dose cohorts, including dose and dosing schedule, are summarized in [Table 1](#). For each cohort, one cycle is 6 weeks. In each cohort, subjects will receive IMC-CS4 by I.V. infusion (with an observation period, in Part A only, for weekly [qw] and every-2-week [q2w] cohorts, in Cycle 1 only, as described in [Table 1](#)). Beginning with Protocol Amendment Version 7.0, enrollment to Part B of the study will start with Cohort 6a, then escalate to Cohorts 7a and 8a. In the event 2 or more subjects on Cohort 6a experience a DLT event, concurrent enrollment of 3 to 6 subjects to each of Cohorts 6b and 6c will start and further dose escalation (that is, to Cohort 7a) will cease. Likewise, the same algorithm will apply for Cohorts 7a and 8a if enrollment to those cohorts occurs. Subjects will be assigned to “b” and “c” cohorts by the Sponsor. Note that there will be no Cycle 1 observation period for Part B cohorts. No intra-subject dose-escalation is permitted for any subject. Dose escalation may be reduced or ceased at any time based on safety and PK behavior.

Table 1. Dose Cohort Assignment

Cohort	Dose Level	Dosing Schedule^a	Cycle 1 Observation Period^b	Number of Infusions
Part A (weight-based dosing)				

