1	2.5 mg/kg	qw	2 weeks (Weeks 5-6)	Cycle 1: 4 Subsequent cycles: 6
2	0.3 mg/kg	qw	2 weeks (Weeks 5-6)	Cycle 1: 4 Subsequent cycles: 6
3	0.6 mg/kg	qw	2 weeks (Weeks 5-6)	Cycle 1: 4 Subsequent cycles: 6
4	1.25 mg/kg	q2w	3 weeks (Weeks 4-6)	Cycle 1: 2 Subsequent cycles: 3
5	1.25 mg/kg	qw	2 weeks (Weeks 5-6)	Cycle 1: 4 Subsequent cycles: 6
Part B (non-weight-based dosing)				
6a	100 mg	qw	None	Cycle 1: 6 Subsequent cycles: 6
6b ^{c,d}	100 mg	qw on Weeks 1, 2, 4, and 5	None (Weeks 3 and 6 are rest)	Cycle 1: 4 Subsequent cycles: 4
6c ^c	75 mg	qw	None	Cycle 1: 6 Subsequent cycles: 6
7a	150 mg	qw	None	Cycle 1: 6 Subsequent cycles: 6
7b ^{c,d}	150 mg	qw on Weeks 1, 2, 4, and 5	None (Weeks 3 and 6 are rest)	Cycle 1: 4 Subsequent cycles: 4
7c ^c	125 mg	qw	None	Cycle 1: 6 Subsequent cycles: 6
8a	200 mg	qw	None	Cycle 1: 6 Subsequent cycles: 6
8b ^{c,d}	200 mg	qw on Weeks 1, 2, 4, and 5	None (Weeks 3 and 6 are rest)	Cycle 1: 4 Subsequent cycles: 4
8c ^c	175 mg	qw	None	Cycle 1: 6 Subsequent cycles: 6

Abbreviations: aEC = approving Ethics Committee; DLT = dose-limiting toxicity;

IRB = Institutional Review Board; PK = pharmacokinetic(s); qw = weekly; q2w = every 2 weeks.

a – At the highest dose level where major toxicity is observed and that requires a longer recovery period between infusions, a change in the periodicity of dosing (that is, other dosing schedules based on safety and PK considerations) will be agreed upon with the Investigator and communicated to IRBs/aECs.

b – Observation following the fourth infusion in Cohorts 1, 2, 3, and 5 (qw dosing) and the second infusion in Cohort 4 (q2w dosing) in Cycle 1 only. No Cycle 1 observation period for Cohorts 6a, 6c, 7a, 7c, 8a, or 8c. Weeks 3 and 6 of all cycles are rest weeks in Cohorts 6b, 7b, and 8b (qw dosing on Weeks 1, 2, 4, and 5).

c – Concurrently enroll to Cohorts 6b/7b/8b and 6c/7c/8c, should ≥ 2 subjects in Cohort 6a/7a/8a experience DLT events.

d – For all cycles: Infusions on Weeks 1, 2, 4, and 5, and rest on Weeks 3 and 6.

It is recognized that in the course of clinical cancer care, it is not always possible to schedule therapeutic infusions at precise intervals (because of holidays, travel difficulties, or other circumstances). Accordingly, infusions administered within 2 days (all cohorts other than q2w

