12.5 Analyses of Safety Data

12.5.1 Extent of Exposure

Exposure analyses will be based on the actual dose administered (in mg) and body weight (in kg) per the eCRF. The baseline body weight will be used for calculating each dose unless the subject's weight changes $\geq 10\%$ from baseline and a dose change is required. Dose intensity and relative dose intensity will be calculated based on the dose administered and the most recent body weight recorded prior to treatment administration. Exposure analyses will include duration of treatment (weeks), number of subjects treated by cycle, number of infusions per subject,

cumulative dose, dose intensity and relative dose intensity, and number (%) of subjects with dose modifications (reduced or delayed).

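### SAP Table 2 no longer matches protocol Table 12, so Cohort 5 dose reductions are miscounted and Part B reductions and relative dose intensity have no usable rule

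*SAP*

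**What the plan says.** **Counting reductions.** SAP 5.2.1.4 compares the dose level entered for each infusion with the "protocol planned dose level as referenced in Table 2: General Dose Reduction Guidelines" and counts the steps between them. The note under SAP Table 2 adds: "Actual dose levels entered in the CRF will be rounded to the nearest dose level listed in this table". Its worked example is in mg/kg and does not mention schedule. The Cohort 5 row of that table starts at "1.25 mg/kg weekly" and steps to 0.6 and then 0.3 mg/kg, both weekly. Table 12 of the current protocol (10.1.2) takes Cohort 5 first to 1.25 mg/kg every 2 weeks and then to 0.6 mg/kg weekly. SAP 5.3.4.2 reports the number and percentage of patients with any reduction, to the first or second level.

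**Exposure.** The SAP sets "Dose intensity (mg/kg/week) = Cumulative dose / Duration of treatment" and divides this by the planned weekly dose from SAP Table 1 to obtain relative dose intensity. For subjects who have started Cycle 2, footnote 5 states that "14 days is subtracted from the duration of cycle because the 2-week observation period is excluded from the duration of treatment". SAP Tables 1 and 2 hold Cohorts 1 to 6 only, all in mg/kg. Their Cohort 6 (2.5 mg/kg every 2 weeks) is not in the current protocol.

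**Part B.** Protocol 4.1 defines nine cohorts, 6a to 8c, dosed in fixed mg. It states: "Note that there will be no Cycle 1 observation period for Part B cohorts". For 6b, 7b and 8b the schedule is: "For all cycles: Infusions on Weeks 1, 2, 4, and 5, and rest on Weeks 3 and 6". Protocol 12.5.1 lists relative dose intensity and dose modifications among the exposure outputs, but it keeps a weight basis ("Dose intensity and relative dose intensity will be calculated based on the dose administered and the most recent body weight") and gives no rule for doses fixed in mg.

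**The concern.** A count of reduction steps is only as good as the ladder it is read from. The SAP ladder for Cohort 5 is not the one that subjects descend under the current protocol: its first protocol step changes the interval and leaves the mg/kg dose alone. That step leads to 1.25 mg/kg every 2 weeks, which protocol 4.1 names as the Part A MTD. A rule that looks only at mg/kg would record a move down to the MTD regimen as no reduction at all.

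Part B has three gaps. It has no row in either SAP table, so neither the number of reductions nor relative dose intensity has a stated derivation. The mg/kg formulas do not suit a flat dose. The duration rule subtracts two weeks for an observation period that Part B subjects do not have. Exposure and dose modification belong to the safety analysis, and the safety profile is a primary objective, so these tables should be right even though they are descriptive.

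**Working it through.** **1. Cohort 5.** The SAP row (Table 2) is 1.25, 0.6, 0.3 mg/kg, all weekly. The protocol steps (Table 12) are 1.25 weekly, 1.25 every 2 weeks, 0.6 weekly. The correct scores for the two reductions are 1 and 2. As a check, scoring the SAP row against itself gives 0, 1, 2, so the rule works when the ladders agree.

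| Reading of dose level | First protocol reduction | Second protocol reduction |
|---|---|---|
| mg/kg per infusion | 1.25 is nearest 1.25: **0** | 0.6 is nearest 0.6: **1** |
| Weekly-equivalent mg/kg | 1.25/2 = 0.625 is nearest 0.6: **1** | 0.6 is nearest 0.6: **1** |
| Exact dose and schedule | 1.25 every 2 weeks is not in the row: **no match** | 0.6 weekly: **1** |

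No reading returns 1 and 2. The first is best supported, because the SAP compares doses infusion by infusion and its rounding example is in mg/kg.

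**2. Cohort 4, for contrast.** The SAP row is 1.25, 0.6, 0.3 every 2 weeks; the protocol steps are 1.25 every 2 weeks, 0.6 weekly, 0.3 weekly. By mg/kg per infusion the two reductions score 1 and 2, which is correct although the schedules differ. By weekly equivalent they score 0 and 1, and by exact match neither is found.

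**3. Effect on the any-reduction percentage.** Under the mg/kg reading, each Cohort 5 subject reduced only to 1.25 mg/kg every 2 weeks is missed. With an assumed cohort of 6 that is 1/6 = 16.7 percentage points; with 3 it is 1/3 = 33.3 points. The cohort size is an assumption from the 3+3 rule, and at least one such subject has to exist. Under the weekly-equivalent reading nobody is missed.

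**4. Part B cohorts that can open.** If the protocol 4.1 algorithm runs to its end, the possible sets are 6a/6b/6c, 6a/7a/7b/7c, 6a/7a/8a, or 6a/7a/8a/8b/8c. That is three to five cohorts and, at two steps each, 6 to 10 reduction steps. None has a row in SAP Table 1 or 2.

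**5. Illustration of the duration rule.** Suppose planned mg doses were added and the rule kept, with its subtraction read as 14 days (2 weeks) as footnote 5 indicates. All doses are given. The planned weekly dose is 100 mg for 6a and 100 × 4/6 = 66.7 mg for 6b.

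| Stop after | Cohort | Total mg | Weeks by SAP rule | mg/week | Relative dose intensity |
|---|---|---|---|---|---|
| Cycle 2 | 6a | 12 × 100 = 1200 | (77 + 7)/7 − 2 = 10 | 120 | 120/100 = 120% |
| Cycle 2 | 6b | 8 × 100 = 800 | (70 + 7)/7 − 2 = 9 | 88.9 | 88.9/66.7 = 133% |
| Cycle 4 | 6a | 2400 | 24 − 2 = 22 | 109.1 | 109% |
| Cycle 4 | 6b | 1600 | 23 − 2 = 21 | 76.2 | 114% |

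A fully dosed subject should show 100%. For 6a after Cycle 2, dropping the subtraction is enough: 1200/12 = 100 mg/week. For 6b it is not: 800/11 = 72.7 mg/week, or 109%. Counting the final scheduled rest week gives 800/12 = 66.7 mg/week, or 100%.

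**The case against.** The strongest reply is that this is one version gap. The SAP was approved in October 2012 for protocol Version 3.0, Part B arrived with Version 7.0, and protocol 12.1 defers detail to a separate SAP, which may since have been updated. That explains the mismatch but does not remove it: no supplied document corrects it, and SAP 5.5 records no changes from the protocol. If a later SAP exists, the sponsor need only confirm that it covers these points. Nor does the mismatch show that Table 2 was wrong when written; the Version 3.0 table is not available for comparison.

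Three further replies limit the point:

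- SAP Table 2 prints a schedule beside every dose, so a programmer might not ignore it. A reader might infer that a Cohort 5 subject is certain to be missed. The documents do not support that, because the weekly-equivalent reading still counts the subject as reduced.
- A reader might count nine uncovered cohorts and 18 uncovered steps. At most five cohorts and 10 steps can arise.
- A reader might take 120% and 133% as what the plan would report. Neither document states that hybrid rule; as written, the plan gives no Part B figure. The 100% benchmark for 6b also rests on counting the final rest week.

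It is also fair to say that the raw information survives. Sites record reductions on the eCRF, the SAP lists modifications and dose intensity by patient, and a move from weekly to every 2 weeks would lower a Cohort 5 subject's relative dose intensity. The summary count would still be wrong or undefined.

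**Conclusion.** The point holds. For Cohort 5, every reading examined labels the second protocol reduction as the first. Under the best-supported reading the first is scored as none, and a subject who goes no further is left out of the any-reduction percentage. That omission depends on taking dose level as mg/kg per infusion, and its size depends on cohort size and on how many such subjects there are; the supplied text gives no number of reduced subjects. For Part B, the reduction count and relative dose intensity cannot be derived from the supplied SAP, and its 14-day subtraction is wrong for those cohorts.

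The reach is limited to descriptive exposure and tolerability tables. It would be wrong to infer that DLT counts or the RP2D are at risk, since neither uses these quantities. The SAP should be corrected before the tables are programmed, but the trial's dose decisions are not in question.

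**What to change.** - Replace SAP Tables 1 and 2 with the current cohorts and the protocol Table 12 steps.
- Define a reduction step by dose plus schedule within the subject's own cohort row, so that a change of schedule alone counts as one step. Cohort 5 then scores 1 and 2.
- Use the steps of the protocol version in force when the subject was reduced. The sponsor holds these versions.
- For Part B, use cumulative dose in mg and dose intensity in mg/week, against planned weekly doses of 6a 100, 6b 66.7, 6c 75, 7a 150, 7b 100 (150 × 4/6), 7c 125, 8a 200, 8b 133.3 (200 × 4/6) and 8c 175 mg/week.
- For Part B, drop the 21-day and 14-day adjustments tied to the Cycle 1 observation period. In 6b, 7b and 8b, count scheduled rest weeks in the duration, including the one after a last infusion in Week 2 or Week 5.
- Record the mg basis in SAP 5.5 as a change from protocol 12.5.1.

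The cost is SAP text only: two tables, the reduction definition, the Part B exposure formulas and one entry in 5.5. No new data are needed, since doses and reductions are already on the eCRF.
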